Remote visits (e.g., at home or at a local medical facility; and via telephone contact from clinical site personnel) will occur every 3 months unless the Investigator deems that a site visit is necessary; urine pregnancy tests will be performed each month for female subjects of childbearing potential (FOCBP).

- **Subjects from Part B Starting Non-Flare-Up Based Treatment During Part C**

Subjects who will start non-flare-up based treatment during Part C will receive non-flare-up based treatment for up to 48 months. These subjects will follow all procedures and undergo all assessments as specified in the Schedule of Assessments in Table 2 of the protocol, including low-dose WBCT scan (excluding head) at Screening and at all annual site visits (Part C Screening and Months 12, 24, 36 and 48.). Non-flare-up Day 1 is the first day that non-flare-up based treatment is initiated during Part C for these subjects.

Remote visits (e.g., at home or at a local medical facility; and via telephone contact from clinical site personnel) will occur every 3 months unless the Investigator deems that a site visit is necessary; urine pregnancy tests will be performed each month for female subjects of childbearing potential (FOCBP).

Blood samples for PK assessment of non-flare-up dosing will be collected at the first 3-month safety assessment at pre-dose and 3, 6, 10, and 24 hours post-dose; if samples cannot be or were not obtained at the 3-month safety assessment, or if a subject is on flare-up based treatment, then the PK blood sample for non-flare-up based treatment can be obtained during any subsequent 3-month safety visit.

Flare-up Based Treatment

Subjects receiving flare-up based treatment will follow all procedures and undergo all assessments as specified in the Schedule of Assessments in Table 3 of the protocol. Assessments will occur at Flare-up Cycle Safety Day 1 at 4 weeks, and every 8 weeks thereafter until treatment of the last flare-up or traumatic event in the flare-up cycle is completed. If after 12 weeks all flare-ups have not resolved then additional treatment and assessments will be performed every 4 weeks until all flare-ups have resolved. All assessments will occur remotely unless the Investigator deems it necessary to evaluate subjects at the clinical site. Once all flare-ups or traumatic events in a cycle have resolved and flare-up based treatment has been completed, subjects will resume non-flare-up based treatment with 5 mg palovarotene once daily

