2.4 Study Populations

A total of approximately 60 subjects will be enrolled in Part C including up to 40 subjects enrolled from Study PVO-1A-201 and up to 20 new adult subjects enrolled during Part B. All subjects will have participated in Part B and no new subjects will be enrolled in Part C and D.

Flare-up Based Treatment Group:

Flare-up based analyses will be based on flare-up cycles in Part C and will include the treatment group combined PVO 20/10 mg.

Combined PVO 20/10 mg is defined as flare-up cycles that flare-ups were treated with PVO 20/10 mg (or weight-based equivalent) during Part C, regardless of whether non-flare-up PVO 5 mg (or weight-based equivalent) treatment had been administered prior to the flare-up dosing.

Non-Flare-up Based Treatment Group:

Non-flare-up based analyses is based on subjects and will include the treatment group with PVO 5 mg (or weight-based equivalent).

PVO 5 mg group is defined as subjects who received at least one dose of non-flare-up regimen (regardless of whether they received the flare-up regimen) during Part C.

Untreated (Never Received PVO Treatment) Group:

Untreated is defined as subjects who were not on the non-flare-up regimen and did not receive flare-up based treatment in Part C.

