2.5 Randomization and Blinding

This is an open-label study and does not involve randomization or blinding.

3 General Statistical Consideration

Categorical data will be summarized with counts and percentages. Percentages will be calculated based on the number of non-missing values and will be reported to one decimal place.

Continuous data will be summarized with descriptive statistics including the number of non-missing values, mean, standard deviation, standard error, median, minimum, and maximum. Minimum and maximum will be reported to the same precision as the raw values, mean and median will be reported to one additional decimal place, and standard deviation and standard error will be reported to two additional decimal places.

Non-flare-up based summaries will be performed based on visits in Table 1 and Table 2 in the protocol.

Flare-up based summaries will be performed based on flare-ups at flare-up visits: Flare-up Day 1, Flare-up Week 4 (28 days), Flare-up Week 12 (Day 84) etc.

To distinguish flare-up based analysis from subject based analysis, m will be used for number of flare-ups and n will be used for number of subjects.

In summary of change from baseline analysis for Enrolled Population, baseline from non-flare-up based treatment will be used for subjects in group PVO 20/10 mg only.

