PROMIS Global Health T-score and changes from baseline (defined in Section 3.1) will be summarized at each scheduled visit with descriptive statistics. Data from adult (both physical health and mental health) and pediatric forms will be summarized separately.

7 Safety Data

Safety data summaries in the final CSR will be based on the safety data presentations in recent documents, including the Safety Update included in the NDA and the Day 90 Safety Update; the primary difference will be that those summaries included data from all palovarotene studies, while the Study 202 presentations will only include data collected in Study 202.

While the majority of content listed below corresponds to the data presentation in the interim CSR, it is also relevant for pooled summaries that will be the basis for the final CSR safety discussion.

Adverse events will generally be presented by treatment period (See Section 7.1 for classification of treatment periods) and in total for the Enrolled Population.

The Principal Safety Set (Principal SS) includes all enrolled subjects with the R206H ACVR1 mutation receiving at least one dose of palovarotene in the current study.

Safety data for flare-up based treatment assessments will generally be presented by group combined PVO 20/10 mg for the Flare-up Treated Population.

For vitals, labs, ECGs, physical examination, linear growth assessment and CSSR, summary for non-flare-up based treatment assessments (at regular scheduled visits) will be presented by groups: PVO 20/10 mg only, PVO 5 mg, PVO Total and Never Received PVO Treatment using Enrolled Population. The PVO 20/10 mg only group only includes subjects who did not take PVO 5 mg.

Assessments obtained in Part D include yearly linear height, knee height, weight, physical exam, vital signs, radiographic assessments of the knee and hand/wrist, low-dose WBCT imaging excluding head, adverse events, and concomitant medications.

Pregnancy and Teratogenicity Assessment

Pregnancy and pregnancy outcomes will be monitored throughout the study

Pregnancy test results for females of child-bearing potential were provided as subject listings.

A listing of pregnancy and pregnancy outcomes will summarize subject results

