7.1 Adverse Events

Adverse events will be recorded from the time informed consent (Part C Study Day 1) is signed through study completion. All AEs will be coded to system organ class and preferred term using will be coded using a current version of MedDRA **Study Drug Related Adverse Events:**

At least possibly related AEs are defined as AEs assessed by the Investigator as possibly, probably, or definitely related to study drug.

Adverse events that require Common Terminology Criteria for Adverse Events (CTCAE) grading (Version 4.03, 14 June 2010) as indicated on the eCRF are considered to be retinoid-associated AEs.

Adverse Events Analysis Periods:

All AEs collected during Part C from the time informed consent is signed are considered as treatment emergent adverse events (TEAEs).

TEAEs will be summarized by period (Non-Treatment Period, Non-Flare-up Treatment Period, and Flare-up Treatment Period, Total Treatment Period) and in total.

a) Flare-up treatment period

Adverse events with start date on or after Flare-up Cycle Day 1 and on or before the date of completion for the Flare-up treatment will be attributed to the Flare-up treatment period.

b) Non-Flare-up Treatment Period

Adverse events with start date on or after first Non-Flare-up dose date in Part C for which the subjects are not undergoing flare-up treatment will be attributed to the Non-Flare-up Treatment Period.

Non-Flare-up Treatment Period is period that subjects taking non-flare-up dose including non-flare-up dose interruption periods. All flare-up cycles are excluded.

c) Non-Treatment Period

Adverse events with start date on or after Study Day 1 that are not attributed to the flare-up or non-flare-up treatments will be attributed to the Non-Treatment Period.

Non-Treatment Period are period that subjects are receiving neither non-flare-up and nor flare-up treatment. In Part C, it is the period starting from Part C Study 1 to the day before first study drug dosing date (regardless of whether non-flare-up or flare-up based treatment), and the period from date of study drug discontinuation to end of study or study discontinuation date.

Adverse Events Summary:

The incidence of the following TEAEs will be summarized with counts and percentages of subjects (overall and by MedDRA system organ class and preferred term):

Adverse Event Variables

Adverse Event Observation Periods

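### Part C regular-visit labs, vital signs and ECGs are columned by whether a subject ever took 5 mg, so the PVO 5 mg column also holds values taken during 20/10 mg cycles and dosing interruptions

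*SAP*

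**What the plan says.** All references are to the Part C SAP.

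- **Columns.** Section 7 (Safety Data), on vital signs, labs, ECGs and some other assessments: "summary for non-flare-up based treatment assessments (at regular scheduled visits) will be presented by groups: PVO 20/10 mg only, PVO 5 mg, PVO Total", together with a never-treated group, in the Enrolled Population. It adds: "The PVO 20/10 mg only group only includes subjects who did not take PVO 5 mg".
- **Who is in the 5 mg column.** Section 2.4: "PVO 5 mg group is defined as subjects who received at least one dose of non-flare-up regimen (regardless of whether they received the flare-up regimen", counted over Part C. This is a property of the subject, not of the visit.
- **Which visits count.** Section 3 (General Statistical Consideration): "Non-flare-up based summaries will be performed based on visits in Table 1 and Table 2 in the protocol". This is a property of the schedule, not of the dose being taken.
- **Overlap is foreseen.** Under Section 2.2, remote visits "will occur every 3 months unless the Investigator deems that a site visit is necessary". The PK rule there provides that "if a subject is on flare-up based treatment, then the PK blood sample for non-flare-up based treatment can be obtained during any subsequent 3-month safety" appointment. Subjects return to 5 mg once a cycle ends.
- **Adverse events are handled by date.** Section 7.1: "Adverse events with start date on or after Flare-up Cycle Day 1 and on or before the date of completion for the Flare-up treatment" go to the flare-up treatment period.
- **Flare-up visits have their own presentation.** Section 7 shows flare-up based assessments under combined PVO 20/10 mg. Sections 7.2 and 7.3 call for separate PCS analyses by visit type and for change from Flare-up Cycle Day 1. Section 7.6 (ECG) specifies only a subject-based change and has no separate-analyses sentence.

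**The concern.** A reader of a table headed PVO 5 mg will take it as the safety profile of chronic 5 mg dosing. As defined, the column mixes three states: on 5 mg, on 20 or 10 mg during a flare-up cycle, and off drug during an interruption. If lipids, lipase, liver enzymes, vital signs or ECG intervals respond to dose, on-cycle values will inflate the apparent rate of abnormality on 5 mg and off-drug values will dilute it. Neither effect can be seen in the table.

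The column for flare-up-only subjects has a related problem. These subjects take drug only during flare-ups, so a vital sign or ECG recorded at a regular visit may have been taken on no drug at all.

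Adverse events and measurements are also treated differently. An adverse event with onset during a cycle is attributed to flare-up treatment, while a laboratory value drawn at a regular visit on the same day is attributed to 5 mg.

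**Working it through.** The plan states no figure to reproduce. The check has two parts.

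**1. Does the plan as written put off-regimen values in the 5 mg column?**

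- A subject enters the column with a single 5 mg dose, whatever flare-up treatment is also taken (2.4).
- A visit enters the regular-visit tables because it is on the protocol's non-flare-up schedule (3).
- A regular 3-month visit can coincide with flare-up treatment. The PK rule defers the PK sample for that reason (2.2), and no comparable rule exists for labs, vital signs or ECGs.
- Dosing stopped for subjects under 14 on 4 December 2019 and for the others around 24 January 2020, and could resume from 26 March 2020 at the earliest (1.2). Treatment was not restarted in children under 14 (2.3). Regular-visit values from that time stay under PVO 5 mg for anyone who had taken 5 mg in Part C.

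So yes. No text removes or reassigns these values.

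**2. How large could the on-cycle share be?**

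Inputs from the SAP are visits every 3 months (365.25/4 = 91.3 days) and a planned flare-up course of 28 + 56 = 84 days, longer if extended or restarted (2.3). Cycles per year are an **assumption**, because the SAP gives none. Cycle starts are taken as unrelated to the visit calendar.

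Chance that one cycle of L days covers at least one 3-monthly visit = min(1, L/91.3):

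- L = 28 (the 20 mg phase alone): 28/91.3 = 0.31
- L = 84: 84/91.3 = 0.92
- L = 112 (one 4-week extension): 1

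Share of a 5 mg subject's regular visits that fall on-cycle = cycles per year × L / 365.25:

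| Cycles per year (assumed) | L = 84 | L = 112 |
|---|---|---|
| 0.5 | 42/365.25 = 11.5% | 56/365.25 = 15.3% |
| 1 | 84/365.25 = 23.0% | 112/365.25 = 30.7% |
| 2 | 168/365.25 = 46.0% | 224/365.25 = 61.3% |

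**Illustration of the effect on a PCS percentage.** The per-visit rates are assumed and the cycle rate is one 84-day cycle a year.

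- 2% on 5 mg and 10% on 20/10 mg: 0.77 × 2% + 0.23 × 10% = 3.84%. Of this, 2.30/3.84 = 60% arose on 20/10 mg.
- 5% on 5 mg and 15% on 20/10 mg: 0.77 × 5% + 0.23 × 15% = 7.30%. Of this, 3.45/7.30 = 47% arose on 20/10 mg.

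These figures show the mechanism and do not estimate what the trial will show. The share off drug because of the interruption cannot be calculated, since restart dates are not given.

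**The case against.** The strongest case on the other side has five parts.

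- **The 20/10 mg data have their own tables.** Flare-up assessments are shown under combined PVO 20/10 mg (7). PCS for labs and vital signs is split by visit type (7.2, 7.3). The laboratory PCS listing carries palovarotene dose and start and stop dates (7.2), so each such value can be traced to its dose. This stands: a reader might infer that the 20/10 mg signal disappears, and for labs and vital signs it does not. But a split by visit type does not clean the 5 mg column, because a regular visit during a cycle remains a regular visit, and a listing does not correct a percentage.
- **A reversed dose contrast is not supported for labs.** A reader might infer that 20/10 mg would look safer than 5 mg. Section 2.2 gives subjects who cannot take non-flare-up treatment annual assessments only, without clinical laboratory tests, so for them there are no regular-visit labs to produce a reversal. This stands. For vital signs and ECGs the flare-up-only column may be off drug, but how often is unknown. At a high cycle rate it would be on drug at many visits.
- **The percentages rest on assumption.** The SAP gives no cycle rate and leaves the assessments at each visit to protocol tables not at hand. If the flare-up schedule replaces the regular one during a cycle, fewer values are affected. This stands, and the shares are shares of visits, not of lab or ECG records.
- **The group is openly defined and the summaries are descriptive.** True, but the heading PVO 5 mg does not carry that definition into the table.
- **Section 7.1 is not a ready-made model.** It counts interruptions of 5 mg as non-flare-up treatment, and its description of the Part C non-treatment period does not name gaps between flare-ups. This stands and shapes the fix.

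**Conclusion.** The point holds for the Part C regular-visit tables of labs, vital signs and ECGs. Followed as written, the plan tabulates values taken during 20/10 mg cycles and during dosing interruptions as PVO 5 mg, so neither that column nor its new-onset PCS percentages can be read as 5 mg safety. Regular-visit vital signs and ECGs in the flare-up-only column may be off drug.

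The gap is widest for ECG. Section 7.6 has no change from Flare-up Cycle Day 1 and no instruction to analyse the two visit types separately. It offers only counts by subject or flare-up as appropriate and a listing of PCS cases with no dosing data specified.

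The size cannot be derived from the SAP. About 12%, 23% and 46% of a 5 mg subject's regular visits would be affected at 0.5, 1 and 2 cycles a year. This assumes 84-day cycles, visits spread evenly, and assessments done on-cycle. Extensions and restarts raise these shares; early stopping lowers them.

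The documents do not support reading this as a lost 20/10 mg signal for labs and vital signs, or as a demonstrated reversal of the dose contrast. The matter is still live for the final report: Section 7 says this content is relevant to the pooled summaries behind the final safety discussion, and Section 10 puts the focus on data after 28 February 2020, a period that begins inside the dosing interruption.

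**What to change.** 1. Assign each regular-visit lab, vital-sign and ECG record to the regimen actually in force on its date: 5 mg, flare-up cycle, or no drug.
2. Define no drug explicitly to include dosing interruptions and, for flare-up-only subjects, the gaps between flare-ups. Do not reuse the Section 7.1 periods unchanged.
3. Present values, changes from baseline and new-onset PCS by that regimen.
4. Relabel the present column as ever 5 mg, with or without 20/10 mg, and keep it as a supplementary view.
5. Add to Section 7.6 the separate flare-up and non-flare-up analysis already specified for labs and vital signs, where ECGs are collected on-cycle.

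The cost is one date merge with the dosing data, which the laboratory PCS listing already needs, and revised table columns. The 5 mg column will hold fewer records per visit.

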7.1 Adverse Events

Adverse events will be recorded from the time informed consent (Part C Study Day 1) is signed through study completion. All AEs will be coded to system organ class and preferred term using will be coded using a current version of MedDRA **Study Drug Related Adverse Events:**

At least possibly related AEs are defined as AEs assessed by the Investigator as possibly, probably, or definitely related to study drug.

Adverse events that require Common Terminology Criteria for Adverse Events (CTCAE) grading (Version 4.03, 14 June 2010) as indicated on the eCRF are considered to be retinoid-associated AEs.

Adverse Events Analysis Periods:

All AEs collected during Part C from the time informed consent is signed are considered as treatment emergent adverse events (TEAEs).

TEAEs will be summarized by period (Non-Treatment Period, Non-Flare-up Treatment Period, and Flare-up Treatment Period, Total Treatment Period) and in total.

a) Flare-up treatment period

Adverse events with start date on or after Flare-up Cycle Day 1 and on or before the date of completion for the Flare-up treatment will be attributed to the Flare-up treatment period.

b) Non-Flare-up Treatment Period

Adverse events with start date on or after first Non-Flare-up dose date in Part C for which the subjects are not undergoing flare-up treatment will be attributed to the Non-Flare-up Treatment Period.

Non-Flare-up Treatment Period is period that subjects taking non-flare-up dose including non-flare-up dose interruption periods. All flare-up cycles are excluded.

c) Non-Treatment Period

Adverse events with start date on or after Study Day 1 that are not attributed to the flare-up or non-flare-up treatments will be attributed to the Non-Treatment Period.

Non-Treatment Period are period that subjects are receiving neither non-flare-up and nor flare-up treatment. In Part C, it is the period starting from Part C Study 1 to the day before first study drug dosing date (regardless of whether non-flare-up or flare-up based treatment), and the period from date of study drug discontinuation to end of study or study discontinuation date.

Adverse Events Summary:

The incidence of the following TEAEs will be summarized with counts and percentages of subjects (overall and by MedDRA system organ class and preferred term):

Adverse Event Variables

Adverse Event Observation Periods

- TEAEs are AEs with (first dose date of study drug during 202 C) \leq (AE start date) \leq (last dose date of study drug +7 days for all AEs, i.e., non-serious and serious AEs).
 - A chronic TEAE is a TEAE with an onset date during chronic treatment
 - A flare-up TEAE is a TEAE with an onset date during flare-up treatment
- Post-treatment AEs are AEs with a start date $>$ last dose date in Part C + 7 days for All AEs (non-serious and serious AEs).
 - Any AEs
 - Any post treatment AEs
 - Any TEAEs
 - Any TEAEs by maximum severity
 - Any TEAEs at least possibly related to study drug
 - Any TEAEs at least possibly related to study drug by maximum severity
 - Any serious adverse events (SAEs)
 - Any TEAEs leading to dose modification
 - Any TEAEs leading to interruption of study drug
 - Any TEAEs leading to discontinuation of study drug
 - Any TEAEs leading to discontinuation from study

Data listings will be provided for

- All TEAEs
- All post treatment AEs

- SAEs
- SAEs for premature physcal closure and bone safety
- Deaths
- TEAEs leading to dose modification of study drug
- TEAEs leading to interruption of study drug
- TEAEs leading to discontinuation of study drug
- TEAEs leading to discontinuation of study
- AEs ongoing at date of informed consent signed in Part C

Part C Study Day and/or Flare-up Day for AE start and stop dates will be included on AE listings as appropriate.

Adverse event severity will be assessed and reported according to criteria defined in the protocol (mild, moderate, severe). Adverse event causality will also be assessed in terms of relationship to study drug and reported according to criteria described in the protocol (not related, possibly related, probably related, definitely related).

Deaths

Deaths after the first dose of study drug are either on-treatment or post-treatment:

- Deaths on-treatment: deaths occurring after the first dose of study drug and up to 7 days after the last dose of study drug
- Death post-treatment: deaths occurring more than 7 days after the last dose of study drug until 30 days after last dose of study drug

The SAE, including death, reporting period for the non-flare-up-based treatment and the flare-up-based treatment begins at the time of informed consent and continues through study completion (including Part D) + 30 days.

7.2 Safety Laboratory Assessments

Blood and urine samples will be collected for hematology, biochemistry (includes lipids), and urinalysis testing.

Females of child-bearing potential must have a negative blood or urine pregnancy test (with sensitivity of at least 50 mIU/mL) prior to administration of palovarotene. A blood or urine pregnancy test will be conducted monthly in Part C.

For females of childbearing status: if pregnancy testing did not continue monthly per protocol post the study drug interruption then at a minimum a self-administered urine pregnancy test is to be done within 4 weeks before re-starting palovarotene treatment.

Values and changes from baseline (defined in Section 3.1) for hematology, biochemistry (includes lipids) parameters will be summarized at each scheduled visit with descriptive statistics. Both the change from baseline (subject based) and the change from Flare-up Cycle Day 1 (flare-up based) will be presented.

The following plots will be provided:

- Boxplots for lab parameter over time by scheduled visits and by flare-up visits.
- Mean percent of normal high for serum chemistry and lipid lab analytes including:
 - Aspartate Aminotransferase (AST)
 - Alanine Aminotransferase (ALT)
 - Gamma Glutamyl Transferase Gamma Glutamyl Transferase (GGT)
 - Creatinine
 - Lipase
 - Bilirubin
 - Triglycerides (lipid)
- Mean percent of normal low for hematology lab analytes including:
 - Hematocrit (HCT)
 - Hemoglobin (HGB)
 - Bicarbonate (HCO₃)

If multiple records occur within a post-baseline visit, the first non-missing value will be used. Note that results obtained locally rather than from the central laboratory will also be used for summaries.

Potentially clinically significant (PCS) values are predefined criteria/thresholds presented in [Table 4](#). PCS values at baseline and new-onset PCS values post-baseline will be summarized with counts and percentages of subjects or flare-ups as appropriate. Separate analyses will be performed for the non-flare-up treatment visits and the flare-up treatment visits. Percentage of incidence of new-onset PCS laboratory values over time will be plotted.

New-onset PCS values are defined as values that were not PCS at baseline (defined in [Section 3.1](#)) and were PCS post-baseline. Note that results obtained locally will be included in these summaries.

Table 4: Potentially Clinically Significant Safety Laboratory Values

	PCS Low	PCS High
Biochemistry		
Aspartate aminotransferase	N/A	3 x ULN
Alanine aminotransferase	N/A	3 x ULN
Amylase	N/A	3 x ULN
Lipase, pancreatic	N/A	3 x ULN
Bilirubin	N/A	>2 mg/dL
AST, ALT and total bilirubin	N/A	AST or ALT > 3 x ULN and total bilirubin > 2 x ULN
Thyroxine	<4.0 mcg/dL	>13.0 mcg/dL
Lipids		
Cholesterol	N/A	>300 mg/dL
Triglycerides	N/A	>400 mg/dL
Hematology		
Leukocytes	<2.8 x 10 ⁹ /L	>16.0 x 10 ⁹ /L
Hemoglobin (females)	<9.5 g/dL	>17.5 g/dL

	PCS Low	PCS High
Hemoglobin (males)	<11.5 g/dL	>19.0 g/dL
Hematocrit (females)	<32%	>54%
Hematocrit (males)	<37%	>60%
Platelets	<75 x 10 ⁹ /L	>700 x 10 ⁹ /L

Urinalysis parameters will be tabulated for Non-Flare-up Treated Population and Flare-up Treated Population.

A listing will be provided for all subjects meeting PCS laboratory criteria that will include all PCS results during the study along with associated palovarotene and glucocorticoid dosing data (dose and start and stop dates). A by-subject listing of all laboratory parameters will be generated. Listing for subjects with PCS lipase values will also be listed separately.

